	
chemistry tests are presented with descriptive statistics by group and visit to examine the trend of change. In the case of urine tests, the frequency and ratio of changes from normal before administration to abnormal after administration are presented by group and visit to examine the trend of change.
 
4) Major adverse cardiac event (MACE) MACE is defined as “cardiac death, myocardial infarction, ventricular arrhythmia requiring treatment, or hospitalization for target vessel revascularization” and comparisons between treatment groups are tested using Fisher’s Exact Test.
 
5) Safety evaluation of intramuscular injection of VM202RY The frequency of persistent bleeding, arrhythmia, and other complications occurring after VM202 administration is presented by administration group, and comparisons between groups are tested using Fisher’s Exact Test.
 
Secondary endpoint
 
- Efficacy evaluation
1) Cardiac function The evaluation of cardiac function (left ventricular ejection fraction by cardiac MRI, myocardial SPECT, and echocardiography) was tested using the Kruskal-Wallis test for group differences in changes before and after VM202RY administration.2) Viable myocardium The evaluation of the size of the viable myocardium (cardiac MRI: myocardial thickness in the VM202RY injection area, extent of gadolinium late enhancement, and exercise intensity in the regional region) was tested using the Kruskal-Wallis test for group differences in changes before and after VM202RY administration.3) Myocardial ischemic area Evaluation of myocardial SPECT (blood flow changes in the injection area at rest and under load) is tested using the Kruskal-Wallis test for group differences in changes before and after VM202RY administration.- HGF concentration in blood Measure and observe plasma HGF concentrations and examine whether there is a correlation between the results and the degree and pattern of adverse reactions.- Anti-HGF antibody production by VM202RY administration Correlation between anti-HGF antibody production and cardiac function improvement is evaluated.
--	---

Schedule of evaluations and visits

[figure not shown]
Procedure	Screening	Treatment					Follow-up				
		Day 0	Day 1	Day 2	Day 5	Day 7	Week 2 (±4D)	Week 4 (±4D)	Week 8 (±7D)	Week 12 (±7D)	Week 24 (±7D)
Visit schedule	-21 ~ -1 day										
Informed consent	X										
Inclusion / Exclusion criteria	X	X									

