According to the WHO Toxicity Scale, toxicities of Grade 3 or higher are generally considered dose-limiting. However, since this clinical trial includes surgery, the following reactions caused by surgery are excluded from the DLT (Dose-Limiting Toxicity) evaluation:

Adverse events caused by coronary artery bypass graft (CABG) surgery are excluded from the DLT evaluation.

1. Hematology

- Hemoglobin: Decrease due to surgical bleeding that recovers with transfusion.
- Hemorrhage: Common post-operative complication. However, persistent bleeding at the gene injection site should result in discontinuation of dose escalation.

2. Gastrointestinal

- Bilirubin: Elevation up to 10.6 due to intra-body retention of hematoma after surgery is considered a normal response.
- GOT/GPT (AST/ALT): Levels up to 125/350 are excluded if attributable to transfusion or myocardial ischemia.

3. Renal / Bladder

- Proteinuria: If caused by pre-existing diabetes or renal failure.
- Hematuria: If caused by trauma during Foley catheter insertion.

4. Pulmonology: Findings due to decreased cardiac function.

5. Fever: Fever above 39°C lasting less than 24 hours (unless associated with pulmonary complications or infection).

6. Allergic Reactions: When the cause is clearly identified, such as contrast agents, antibiotics, or blood transfusion.

7. Cardiac

- Rhythm: Arrhythmias are unavoidable due to surgical dissection of the myocardium. While ventricular arrhythmias may occur due to reperfusion of chronically ischemic areas, establishing a direct association with gene injection is difficult. However, in the interest of patient safety, WHO Grade 3 criteria will be followed and dose escalation will be discontinued.
- Cardiac Function: Most patients have impaired cardiac function due to the nature of cardiac surgery; thus, excluded from DLT evaluation.
- Pericarditis: Most cases involve post-operative accumulation of blood or fluid in the pericardial space. Surgery may be necessary, but dose escalation will be discontinued only if bleeding is confirmed at the gene injection site.

2) TD (tolerated dose) evaluation

Subjects are enrolled sequentially, starting from Step 1, to determine the tolerated dose as follows:

1. Step 1: Three subjects are enrolled. DLT (Dose-Limiting Toxicity) is evaluated 4 weeks after the third subject is dosed.
 - 1-1. If no DLTs occur in any of the 3 subjects (0/3) → Proceed to Step 2 and enroll 3 more subjects (A)

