All adverse events, clinical laboratory test results, and vital signs (blood pressure, temperature, pulse, respiration) of the study subjects will be summarized in tables and reviewed comprehensively to assess dose-dependent trends. All clinically significant abnormal laboratory results should be recorded in the adverse event section of the case report form (CRF), and the severity, course, and relationship to the investigational drug must also be documented.

As the number of subjects assigned per dose group in a Phase I clinical trial is small, the determination of normal or abnormal laboratory test results will be made on a per-subject basis. Statistical validation may be performed if necessary. In particular, adverse events that are anticipated or listed in the precautions for use must be closely monitored for changes, and if observed, should be tabulated by dose group for comparative analysis.

- ① Since the test subjects have not previously been exposed to the investigational substance, pre-treatment allergy and anaphylaxis testing methods are considered not meaningful. In addition, as the vector was manufactured using kanamycin instead of ampicillin, skin testing is also deemed unnecessary. Furthermore, as the investigational agent is an angiogenic substance, skin testing may potentially induce angiogenesis in the skin and is thus discouraged.
- ② Although the concentration of HGF in the blood is expected to be minimal following intramyocardial injection, due to concerns about retinal neovascularization, fundoscopy will be performed before surgery and during the follow-up period to assess potential retinal lesions.
- ③ Cardiac MRI will be used to monitor for the development of intramyocardial hemangiomas.
- ④ The occurrence of ventricular arrhythmia will be monitored via continuous ECG during hospitalization and regular ECG during the follow-up period.

All adverse events and their severity by dose group will be presented, and incidence rates along with 95% confidence intervals will be estimated. If feasible, Fisher's Exact Test will be used for comparisons.

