Vital signs (blood pressure, temperature, pulse, respiration) will be summarized with descriptive statistics by group and visit to evaluate trends. Physical examination findings will identify abnormal findings before and after administration, presented by group. For laboratory tests (general hematology and chemistry), descriptive statistics will be provided by group and visit to observe trends. For urinalysis, changes from normal (pre-dose) to abnormal (post-dose) will be presented by group and visit to assess trends.

4) Major Adverse Cardiac Event (MACE)

In this study, MACE is defined as cardiac death, myocardial infarction, ventricular arrhythmia requiring treatment, or hospitalization for target vessel revascularization. Investigators must monitor and confirm the occurrence of MACE. Any MACE must be reported to the sponsor in accordance with serious adverse event reporting guidelines. Inter-group comparisons of MACE incidence will be analyzed using Fisher's Exact Test.

5) Safety assessment of VM202RY intramyocardial injection

The safety of VM202RY intramyocardial injection will be evaluated by monitoring for persistent bleeding, arrhythmia, and other complications. Investigators must closely observe subjects for these events following VM202RY administration. The incidence of persistent bleeding, arrhythmia, and other complications will be presented by treatment group, and inter-group comparisons will be performed using Fisher's Exact Test.

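### The urinalysis summary counts only normal-to-abnormal changes, so worsening of an item already abnormal at baseline is not shown there and is seen elsewhere only if judged a clinically significant adverse event

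*Combined protocol and SAP*

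**What the plan says.** Laboratory results are part of the primary safety endpoint (Synopsis, Endpoints; section 17.3.2). The plan treats them as follows.

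- **Urinalysis.** Section 17.3.3, item 3: "For urinalysis, changes from normal (pre-dose) to abnormal (post-dose) will be presented by group and visit to assess trends". The Synopsis (Statistics) says that "the frequency and ratio of changes from normal before administration to abnormal after administration are presented by group and visit".
- **Blood tests.** Section 17.3.3, item 3: "For laboratory tests (general hematology and chemistry), descriptive statistics will be provided by group and visit to observe trends". The plan does not list which statistics, and it names no shift table.
- **Level of judgement.** Because the groups are small, "the determination of normal or abnormal laboratory test results will be made on a per-subject basis".
- **General tabulation.** "All adverse events, clinical laboratory test results, and vital signs" are all to be tabulated and reviewed for dose-dependent trends.
- **Adverse event route.** Clinically significant abnormal laboratory results go into the adverse event section of the CRF with severity, course and relationship. Sections 17.3.3 and 18.1 both count worsening as an adverse event, and section 18.1 grades events on the WHO scale where it applies. All events are presented by severity and dose group, with incidence and 95% CI.
- **DLT.** Among the surgery-related reactions removed from the DLT evaluation is "Proteinuria: If caused by pre-existing diabetes or renal failure".

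**The concern.** A count of normal-to-abnormal changes can register only items that were normal before dosing. The plan itself expects some that were not. Diabetes is not an exclusion and is recorded as medical history (section 14.1). Exclusion 15 removes creatinine above 2 mg/dL, anuria, acute renal failure and dialysis, so milder renal impairment can enter. The DLT section anticipates proteinuria from diabetes or renal failure.

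For those subjects, a urinalysis item can worsen by two WHO grades and leave the urinalysis display unchanged. The same proteinuria can also be left out of the DLT count if it is attributed to the pre-existing disease. The only remaining route into a summary table is the investigator's judgement of clinical significance, made in an open-label trial without a stated criterion. What is at stake is whether the laboratory part of the primary safety report shows such a change in a trial where each cohort has only a few subjects.

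**Working it through.** **Group sizes.** Section 11.4 plans 3 subjects in each of three dose groups and allows 18 in all if DLTs occur. 3 × 3 = 9 and 3 × 6 = 18, so the plan's figures reproduce. A group can therefore have 6 subjects, before any replacement of dropouts.

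**What the urinalysis count can see**, for one item in one subject:

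| Baseline | Post-dose | Counted? |
|---|---|---|
| Normal | Normal | No |
| Normal | Abnormal | Yes |
| Abnormal | Normal or same | No |
| Abnormal | Worse | No |

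The last row is the gap. The per-subject judgement does not close it: it sorts results into normal and abnormal, and this subject is abnormal both times.

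**Hypothetical cohort of three, proteinuria.** Baseline 0, 0, 1+; worst post-dose 0, 0, 4+. In Appendix 5, 1+ is Grade 1 and 4+ is Grade 3.

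- Planned count: 0 + 0 + 0 = 0 changes. Only 2 of the 3 subjects could have contributed. The Synopsis does not define the denominator of its ratio, but 0/3 and 0/2 are both zero.
- Shift table: 1 of 3 = 33% worsened, shown as Grade 1 to Grade 3.

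**Adverse event table, same cohort.** The plan names no CI method; exact (Clopper-Pearson) limits are used here.

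- Judged clinically significant: 1/3 = 33%. The lower limit is 1 − 0.975^(1/3) = 0.8%. The upper limit is the 97.5% point of Beta(2, 2) = 90.6%.
- Not so judged, and no other case: 0/3. The upper limit is 1 − 0.025^(1/3) = 70.8%.

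So the same urine results are reported as 1/3 or 0/3 depending on one undefined judgement. Even when the event is recorded, the table as described gives its severity and not the baseline grade, so it does not show the shift.

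**DLT.** The exclusion applies to proteinuria caused by pre-existing diabetes or renal failure. It removes such a case from the DLT evaluation only; nothing removes it from adverse event recording.

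**Blood tests, for comparison.** Hypothetical creatinine in mg/dL: 0.9, 1.0, 1.6 before and 0.9, 1.0, 3.2 after.

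| | Before | After |
|---|---|---|
| Mean | 3.5/3 = 1.17 | 5.1/3 = 1.70 |
| SD | 0.38 | 1.30 |
| Median | 1.00 | 1.00 |
| Maximum | 1.6 | 3.2 |

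The median hides the doubling. The mean, SD and maximum reveal it, though without linking it to a subject's baseline. What a reader sees depends on which statistics are chosen, and the plan leaves that open.

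**The case against.** The strongest reply is that the plan has a second route. Worsening is an adverse event by definition, clinically significant laboratory abnormalities are recorded as such, and every event is tabulated by severity and dose group. A rise from 1+ to 4+ would be a Grade 3 event, and an investigator would be unlikely to dismiss it. Section 18.1 also requires two or more investigators to assess causality for a DLT or an unexpected event of Grade 3 or higher. This stands in large part. A reader might infer that worsening from an abnormal baseline appears in no summary table; the documents do not support that. What remains is that the route depends on a judgement with no stated criterion. It is least secure for smaller rises and for proteinuria already ascribed to known disease.

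A reader might also infer that blood tests are summarised only as means of three subjects. The text says descriptive statistics without restricting them, and a group can reach six. The promise of per-subject judgement is a safeguard, not a contradiction.

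Nor do the documents support saying that the display biases the safety conclusion towards no effect, or that these subjects are most at risk. Section 13.4.6 reports no toxic changes in the animal studies. The injection-related concerns in section 18.2 are bleeding, retinal lesions, haemangioma and ventricular arrhythmia.

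Finally, this could be called a preference about table format. That is fair as to scale. But the plan names a specific statistic for a primary safety item, and a better one is available from data it already collects.

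**Conclusion.** The point holds in a limited form. Followed as written, the urinalysis summary cannot show worsening of an item that was abnormal at baseline. Such worsening is visible elsewhere only if the investigator judges it a clinically significant adverse event, and proteinuria attributed to pre-existing diabetes or renal failure is also outside the DLT count.

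In the worked cohort the difference is 0 against 1 of 3 subjects. Those values are illustrative. The documents do not say how many subjects will have an abnormal screening urinalysis, so no expected number of missed cases can be given. The gap also applies item by item: the plan does not say that one abnormal item removes a subject from the whole display, so a subject with baseline proteinuria can still contribute for haematuria.

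This is a minor point and a free improvement. It concerns the reporting of a primary safety item. It does not change the data collected, the DLT definition, the escalation rule or the tolerated dose.

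**What to change.** In the Synopsis (Statistics, item 3) and section 17.3.3, item 3, replace the normal-to-abnormal count with a shift from baseline to worst post-dose category. Present it item by item and per subject, and also by visit.

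- Use WHO grade where Appendix 5 gives one (proteinuria and haematuria) and dipstick category for the other items.
- State the denominator: subjects with a baseline and at least one post-dose result for that item.
- Optionally, set the same WHO-grade shift beside the descriptive statistics for the haematology and chemistry items that Appendix 5 grades, and list which statistics will be shown. With 3 to 6 subjects per group, a per-subject display is easy to read.

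The cost is a change of wording and one table shell. Urinalysis is already scheduled at screening, during the hospital stay and at Weeks 2, 4, 12 and 24, and the grading scale is already appended. No visit, sample or clinical rule changes.

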17.4 Secondary endpoint: efficacy

Although the primary objective of this Phase I clinical trial is to assess safety, considering that the subjects are severely ill patients and will be followed for a long period (6 months), it is deemed reasonable to also observe efficacy. Therefore, exploratory efficacy evaluation will be conducted as follows, only when such assessment is possible.

17.4.1 Efficacy evaluation population

Both Per-Protocol (PP) and Intention-to-Treat (ITT) analyses will be performed, and the target populations are as follows:

1) Subjects included in the Intention-to-Treat (ITT) analysis

Subjects who received the investigational product and for whom efficacy assessment is possible, regardless of protocol violations or adherence to visit schedules.

2) Subjects included in the Per-Protocol (PP) analysis

- ① Subjects who did not violate the inclusion/exclusion criteria (i.e., eligible patients)
- ② Subjects who completed administration according to the scheduled timing, method, and dosage
- ③ Subjects who were observed for at least 8 weeks after investigational product administration
- ④ Subjects with no missing data in the primary efficacy evaluation parameters
- ⑤ Subjects with no major protocol violations that could affect efficacy assessment (e.g., use of prohibited concomitant medications)

17.4.2 Efficacy evaluation parameters

- 1) Changes in cardiac function
- 2) Size of viable myocardium
- 3) Changes in the myocardial ischemic region

17.4.3 Methods and criteria for efficacy evaluation

- 1) Changes in cardiac function

Changes in cardiac function can be evaluated using the left ventricular ejection fraction (LVEF) measured by cardiac MRI, myocardial SPECT, and echocardiography. Differences between treatment groups before and after VM202RY administration will be tested using the Kruskal-Wallis test.

Cardiac MRI methods and criteria

Analysis will follow the standard cardiac MRI protocols of the Department of Radiology at Seoul National University Hospital, using an appropriate segment model based on the patient's heart size. Parameters evaluated will include left ventricular volume (mL), wall motion index, myocardial thickness (mm), and LVEF (%). Comparisons will be made between baseline and follow-up measurements for each patient, as well as between treatment groups.

Myocardial SPECT methods and criteria

A 20-segment model, similar to the MRI analysis, will be used. Blood flow in each coronary artery distribution area will be assessed using a Bull's-eye view. Perfusion (%) will be evaluated from stress and rest images obtained using Dipyridamole. Additionally, the degree of systolic wall thickening (%), left ventricular volume, and function over time will be compared between groups. Left ventricular volume (mL), ejection fraction (%), and cardiac output (mL) obtained from SPECT will be used as supplementary data. Wall motion indices before and after surgery will be compared. Criteria for determining perfusion deficits and reversibility will follow established standard methods.

Echocardiography methods and criteria

From transthoracic echocardiography, left ventricular diameter (mm), ejection fraction (%), and wall thickness (mL) will be measured and compared with follow-up results after surgery. The Wall Motion Score Index will be calculated by dividing the myocardium into 16 segments and assigning a score to each area based on motion: [1 = normal, 2 = hypokinetic, 3 = akinetic, 4 = dyskinetic]. The total score for the entire myocardium and the right coronary artery region will be averaged by the number of segments.

- 2) Size of viable myocardium

Using cardiac MRI, the myocardial thickness at the gene injection site, the extent of late gadolinium enhancement, and local wall motion strength will be evaluated. Differences between groups before and after VM202RY administration will be tested using the Kruskal-Wallis test.

3) Improvement in Myocardial Ischemia

This will be assessed using myocardial SPECT (changes in blood flow in the gene injection region at rest and under stress). Group differences before and after VM202RY administration will be evaluated using the Kruskal-Wallis test.

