13.3 Allocation method for study cohorts

To evaluate the safety and determine the appropriate therapeutic dosage of VM202RY administered via intramyocardial injection during coronary artery bypass graft (CABG) surgery, the study will be conducted using the following three groups:

(1) Cohort 1

VM202RY 0.5 mg/1 mL will be injected into 4 sites (0.125 mg/0.25 mL per injection point) within the area of incomplete revascularization after CABG.

(2) Cohort 2

VM202RY 1 mg/2 mL will be injected into 8 sites (0.125 mg/0.25 mL per injection point) within the area of incomplete revascularization after CABG.

(3) Cohort 3

VM202RY 2 mg/4 mL will be injected into 8 sites (0.25 mg/0.5 mL per injection point) within the area of incomplete revascularization after CABG.

This clinical trial is an open-label study. It will begin with the lowest dose group, followed by a 4-week follow-up to evaluate safety and therapeutic effect before proceeding to the next higher dose group.

Subjects will be enrolled in the order in which they provide informed consent. To ensure safety, subjects within the same dose group will not undergo CABG and gene therapy at the same time. That is, in each dose group, the gene therapy for the next subject will begin only after the previously enrolled subject has undergone gene therapy and follow-up evaluation has commenced.

The estimated overall duration of the clinical trial is outlined in the following table

	CABG & gene therapy										
		Follow-up									
Day	4 months			4 months			4 months				
Cohort 1 (0.5 mg)	Screen	Treatment	Safety review		End of study						
Cohort 2 (1 mg)				Screen	Treatment	Safety review		End of study			
Cohort 3 (2 mg)							Screen	Treatment	Safety review		End of study

Long-term follow-up will be managed separately from the results of this clinical trial.

13.4 Preparation, dosage, administration method, and handling of the investigational product used in the clinical trial

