18.5 Follow-up management of adverse drug reactions

The principal investigator or responsible person must observe and document all adverse drug reactions related or possibly related to the investigational product that occur during the clinical trial period (from drug administration through follow-up). Monitoring should continue until the adverse reaction returns to baseline or normal levels, the investigator determines the reaction has resolved, or further observation is deemed unnecessary. Upon resolution of the adverse drug reaction, it must be reported to the MFDS. Whenever possible, the reason for discontinuation, treatment provided, and other course details should be investigated. If the subject does not visit in person, follow-up should be conducted via phone or mail.

19. Quality control and assurance of the clinical trial

Before the start of the trial, ViroMed staff, investigators, trial coordinators, and monitors will hold an Investigator's Meeting or Initiation Visit. Detailed discussions will be conducted on the protocol, trial procedures, case report form completion, and specimen collection methods.

Evaluators will receive appropriate training on assessment methods and tools during the Investigator's Meeting or Initiation Visit. Evaluators unable to attend prior training or joining later in the trial will receive training from the investigator or a designated person.

CMIC Korea and ViroMed will provide the trial sites with relevant guideline documents, and monitors will conduct monitoring according to those guidelines. Periodic site visits will be performed to compare source documents with case report forms and verify that the investigator conducts the trial according to the protocol and regulations, ensuring quality control. Communication with site investigators will also occur via mail, phone, and fax. After retrieving case report forms for subjects who have completed the trial, data review will be conducted.

All data will be verified by double data entry into the database. All source documents will be reviewed and corrections made to data entries. After data entry completion, logical checks will be run to identify inconsistent dates or lab test results outside normal ranges. All necessary database corrections will be documented in appendices or audit trails.

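### Nothing in the plan keeps image readers from knowing the dose cohort, although some efficacy readings are judgements compared between cohorts; coded, shuffled reading would be a cheap improvement

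*Combined protocol and SAP*

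**What the plan says.** Section 13.3 states "This clinical trial is an open-label study" and, on the order of cohorts, "It will begin with the lowest dose group". Dose groups therefore follow one another in calendar time.

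Section 17.4.3 describes the imaging measures:

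- **Echocardiography.** The wall-motion index uses 16 segments and is built by "assigning a score to each area based on motion". Grades run from 1 (normal) to 4 (dyskinetic) and are averaged over segments.
- **MRI.** On the reading rules: "Analysis will follow the standard cardiac MRI protocols of the Department of Radiology at Seoul National University Hospital". The segment model is chosen patient by patient, in the plan's words "using an appropriate segment model based on the patient's heart size". On use of the results: "Comparisons will be made between baseline and follow-up measurements for each patient, as well as between treatment groups".
- **Viable myocardium and ischaemia.** MRI thickness, late enhancement and local wall motion at the injection site, and SPECT blood flow in the injected region, are each compared between groups by the Kruskal-Wallis test.

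On the people who make the assessments, section 19 says "Evaluators will receive appropriate training on assessment methods and tools". The documents as released say nothing about masking of readers, reading order or a second reader. Efficacy is exploratory under section 17.4, but section 8.1 links therapeutic effect to the search for the optimal dosage.

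**The concern.** A wall-motion grade depends on the reader's eye, and so to some degree do the extent of late enhancement and the thickness and motion of a region that someone must first identify as injected. A reader who knows that a scan comes from the highest dose may score it a little more favourably. That pushes in the same direction as a true dose effect. With three patients per cohort and no control group, the two cannot be separated afterwards unless the scans are read again.

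At stake is how the secondary efficacy results are interpreted, in particular any statement that a higher dose looked better.

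**Working it through.** **The plan's own figure.** Section 11.4 sets 3 patients per dose group, so 3 × 3 = 9, with a maximum of (3 + 3) × 3 = 18. Both reproduce. They rest on no power calculation; section 11.4 says the trial is not meant to test hypotheses. No significance level, SD or reader variability is stated, so the 5% level and the shifts below are assumptions.

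**Null distribution of the planned test.** For three groups of 3, H = 12/(9 × 10) × Σ(Rⱼ²/3) − 30, where Rⱼ is the rank sum of group j. There are 9!/(3!)³ = 1,680 equally likely allocations. H ≥ 5.6 has exact probability 0.050, and this is used as the critical value.

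**Effect of cohort knowledge.** Simulate normal change scores with no drug effect. Add a reader shift of 0, b and 2b SD to Cohorts 1, 2 and 3.

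| Shift b per dose step (assumed) | Kruskal-Wallis rejects, 3 per group | Cohort means rise in dose order |
|---|---|---|
| 0 | 5% | 17% (exactly 1/6) |
| 0.25 SD | 7% | 31% |
| 0.5 SD | 12% | 48% |
| 0.75 SD | 21% | 65% |

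With 6 per group (the 18-patient maximum), the rejection rate at 0.5 SD is about 25%. A larger sample makes the same reader shift easier to mistake for an effect.

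**Effect of visit knowledge.** A shift that is equal in all cohorts leaves Kruskal-Wallis at 5%. It inflates before-after change instead: a pooled t-test on 9 patients goes from 5% to 26% at 0.5 SD. The plan names no such test, so this figure is only illustrative.

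**Scale of the echocardiographic index.** One segment graded one step differently moves the 16-segment average by 1/16 = 0.0625. If the SD of change were 0.1, 0.2 or 0.3 (assumed), that is 0.63, 0.31 or 0.21 SD. Shifts within the range of the table would then need only about one segment per dose step.

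**Reading load.** The visit schedule gives 3 MRI (screening, Weeks 12 and 24), 3 SPECT (same visits) and 4 TTE (these plus Day 7): 10 studies per patient, so 90 for 9 patients and 180 for 18.

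**The case against.** The strongest reply is that the plan is silent, not wrong. A reader might infer that images are scored with cohort and visit known. No passage says so, and the staff pages were removed from the released document. All that can be said is that nothing prevents it.

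Other parts of the reply also stand:

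- The simulated rates apply to measures for which Kruskal-Wallis is specified, such as LVEF, the MRI injection-site measures and SPECT flow. No test is named for the echocardiographic index. LVEF and SPECT perfusion may depend less on the reader than a wall-motion grade does; the documents do not say how automated they are.
- The MRI segment model is chosen by heart size, not dose.
- Before-after change is confounded by the bypass surgery in every patient, so masking the visit would not make it interpretable. Follow-up scans may also be recognisable as post-operative.
- The same scans serve safety: MRI is used to look for haemangioma, and the Day 7 TTE bears on discharge. Readers may remember them.

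A reader might also infer a threat to escalation, since section 13.3 has therapeutic effect evaluated during the 4 weeks before the next dose group. The documents do not support that. The stopping criteria in section 13.4.6 are DLT, cancer and proliferative retinopathy, section 17.3.3 sets the tolerated dose from DLTs, and neither uses an imaging result.

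What the reply does not remove is the comparison between dose groups. There, knowledge of the cohort can imitate the effect being looked for, and the cohort can be masked.

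**Conclusion.** The point holds as a low-cost improvement, worth making but not essential to the trial's primary purpose. Nothing in the plan stops readers from knowing the dose cohort when they make judgement-based readings that are then compared across cohorts. Under assumed shifts of 0.25 to 0.75 SD per dose step, false rejection rises from 5% to between about 7% and 21% with 3 per group. The visible pattern, which at this sample size will weigh more than any p-value, changes more: at 0.5 SD, rising cohort means become nearly three times as common (48% against 17%). These sizes depend wholly on the assumed shifts; at the low end the effect on the test is small.

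Only knowledge of the cohort can create a dose trend; knowledge of the visit affects before-after change. The primary safety endpoint, the tolerated dose and the escalation rules are untouched.

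**What to change.** Add to section 17.4.3, for the exploratory efficacy analysis only:

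1. The readers already used for each modality score coded MRI, SPECT and TTE files in shuffled order, with cohort and scan date removed.
2. The segments counted as injected are fixed from the operative record before the read. They are supplied without the dose or the number of injection sites, because section 13.4.3 uses 4 sites in Cohort 1 and 8 in Cohorts 2 and 3, so the count would reveal Cohort 1.
3. Safety reads stay immediate and unmasked.

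If this is not done, report unmasked reading as a limitation of any dose comparison.

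**Cost.** No extra patient, scan or visit is needed. Someone must code the files, and about 90 studies (180 at the maximum sample size) must be read as a batch. The documents give no cost and do not identify the readers, so using the same readers and calling the cost low are assumptions. Efficacy results arrive later, readers may recall scans already seen for safety, and pre- versus post-surgery status may remain recognisable. Cohort, and Week 12 versus Week 24, are easier to hide.
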